discontinuation and the rarity of follow-up opportunities in community practice. A more integrative model of ketamine's impact—in particular, anticipated increases in flexible processing across cognition, information processing, and neural networks—reveals a previously unforeseen opportunity to test for synergistic effects when ketamine is coupled with a brief, automated cognitive training intervention designed to consolidate beneficial forms of cognitive processing while neuroplasticity is high. Thus, this project will push the boundaries of how rapid-acting agents could be used clinically, i.e. as short-term cognitive flexibility enhancers. Here, rapid-acting pharmacology becomes merely the first step in a novel treatment algorithm designed to foster relief that is both rapid and durable, simultaneously taking advantage of technology's potential for low-cost, portable, safe, dissemination-ready intervention. Consistent with findings suggesting gold-standard behavioral treatments can prevent depression relapse in the absence of ongoing care, and preliminary evidence that brief cognitive training approaches can likewise have enduring effects over 1-year, we propose that the introduction and facilitation of new learning during a ketamine-induced window-of-opportunity will provide an efficient path to relief that is both rapid and enduring.

Study Objectives

This project seeks to identify the neural and cognitive changes that accompany rapid relief from depressive symptoms following intravenous ketamine. We will then test whether these changes promote the uptake of helpful information delivered by a computer-based training protocol. This work could ultimately lead to the ability to treat depression more efficiently by rapidly priming the brain for helpful forms of learning.

Study Design & Methods

This study is a randomized, double-blind, parallel arm, controlled trial. A target sample size of 150 patients exhibiting the target deficits (negative self-representations and elevated depressive symptoms) will be randomized 2:1 to intravenous ketamine (0.5mg/kg) or saline, followed by either a computer-based cognitive training protocol designed to implicitly instill positive self-representations via Evaluative Conditioning (n=100 drawn from either the ketamine or saline groups) or a sham variant (n=50, from the ketamine group only). Both males and females age 18-60 will be enrolled.

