- General demographic and medical history forms
- Medical intake and comprehensive screening assessments performed by clinical research staff at Bellefield Towers or [name] (Oxford Building). Findings will be reviewed for eligibility and signed by a board-certified physician co-investigator ([name]) prior to the infusion. A drug test will also be obtained at intake; urine pregnancy tests may be obtained prior to fMRI scans at the MRRC.

Screening/baseline procedures include pre-infusion psychiatric evaluation, medical screening, and assessment battery (depression/emotional functioning assessments, neuroimaging, cognitive tasks)=1-2 visits over approximately 1-3 weeks

Infusion (ketamine or saline) visit (“Intervention Day 1” in consent form)=one visit, completed within approximately 1 week of baseline assessments

24-hours post-drug assessment battery (“Intervention Day 2” in consent form) (depression/emotional functioning assessments, neuroimaging, cognitive tasks)=one visit completed 24-hours after drug infusion

Cognitive training sessions and brief assessment battery (“Intervention Days 2,3,4,5” in consent form) (depression and suicidality assessments)=eight 15-20min sessions completed 2x/day (sessions separated by >=20 min) on days 1-4 post-infusion

Infusion +5-days assessment battery (“Intervention Day 6” in consent form) (depression/emotional functioning assessments, neuroimaging, cognitive tasks)=one visit completed following completion of all cognitive training sessions

Infusion +7 days remote (questionnaire) assessment (depression assessments)

Infusion +12 days assessment battery (depression/emotional functioning assessments, cognitive tasks)

Infusion +21 days remote (questionnaire/phone) assessment (depression and suicidality assessments)

Infusion +30-days assessment battery (depression/emotional functioning assessments, neuroimaging, cognitive tasks)

Infusion +2, 3, 4, 5, 6 & 12-months remote, naturalistic follow-up assessments (depression/emotional functioning assessments)=questionnaires completed monthly 2-6 months post-infusion and then once more at 12-months follow-up

Total duration of acute study period (after screening is completed)=approximately 4-5 weeks. Includes 1 infusion visit, 5 in-person assessment visits, 2 remote assessments, and 8 brief cognitive training sessions (twice-daily for 4 days post-drug infusion).

Total duration of naturalistic follow-up period=1-year.

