****Revised/additional exclusion criterion added on IRB's instruction, effective 08/07/2020 through the end of study****

- 19) Patients with diabetes

Rationale: For the duration of the COVID-19 pandemic, patients with diabetes, who are increased risk of serious complications from COVID-19 exposure, will be excluded.

Statistical Considerations and Statistical Analysis Plan

Sample Size

150 depressed adults will be enrolled in the study and randomized to one of the three treatment arms: ketamine + cognitive training (n=50); ketamine + sham training (n=50); or saline + cognitive training (n=50). Enrollment will continue until a final sample is acquired that includes the full target of n=150 patients who complete, at a minimum, (1) an infusion day, (2) a 24-hour assessment visit, and (3) $\geq 75\%$ of intended Neurocognitive Training (active or sham NT) visits, and will thus be considered to have received their NT allocation.

Power Analyses

Previous studies comparing intravenous ketamine to inert and psychoactive comparators (e.g., midazolam) report large effects at 24-hours ($d=.80$ for depression; $d>3$ for brain activation). The PI's previous mechanistic CT study in depression found large effects ($d=.7-1.0$) on symptom and performance-based cognitive measures. Clinically, we are interested in observation of moderate-large effects. The proposed design will yield 80% power to detect moderate effects based on comparisons of 100 ketamine and 50 saline patients ($d\geq .49$ and $r\geq .31$ using $\alpha=.05$). Based on comparisons of 50 patients in each of the ketamine+CT, ketamine+sham, and saline+CT conditions and 80% power, effects of $d\geq .57$ will be detectable (using $\alpha=.05$). Power for primary mixed effects analyses comparing treatment groups, which increases with additional repeated measures, will be higher than for such post-hoc single-point contrasts.

Analytic Plan

Infusion Phase. Mixed models regression with timepoint (baseline, infusion+24-hours) as a continuous within-subject factor, drug condition (ketamine vs. saline) as a fixed between-subject factor, and subject as a random factor will be applied to test hypothesized time*drug interactions on outcomes. For outcomes where time*drug interactions are observed, direction of effects within each drug condition will be disambiguated using baseline vs. post-infusion contrasts.

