Neurocognitive Training Phase. Mixed models regression with timepoint (24-hrs to 30 days) as a continuous within-subject factor, condition (ketamine+NT, ketamine+sham, saline+NT) as a fixed between-subject factor, and subject as a random factor will be applied to test hypothesized treatment and time*treatment interactions on outcomes. Saline+CT will serve as the reference group to test for enduring (main) effects of treatment and for time*treatment interactions.

Exploratory analysis 1 will extend mixed models analysis of depressive symptoms into the 12-month naturalistic follow-up using self-report (primary self-report outcome=QIDS-SR).

Exploratory analysis 2 will utilize a validated data-driven approach to identify integrative/combined moderators of CT effects (DV=MADRS slope), quantified as the optimal weighted combination of moderators (via elastic net w/cross-validation) across all primary + exploratory indices (e.g., fMRI, HNK/BDNF levels, etc.) assessed after ketamine (n=100), defining the data-driven, integrative brain state that optimizes benefit from CT.

Sensitivity analyses will be applied to all hypotheses to explore the impact of main and moderating effects of key biological variables: sex (stratified at randomization to ensure ~60%

female within-cell), age; and baseline clinical variables: treatment-resistance (stratified), concurrent medication.

Exploratory analyses will probe for generalization to other neurocognitive indices and self-report measures [e.g., depressive schemas (CTI); PROMIS measures; QIDS-SR; WHO Disability Assessment Scale].

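### Exploratory analysis 2 names only post-ketamine indices as moderators, so it cannot separate a change after ketamine from a stable pre-infusion trait

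*Combined protocol and SAP*

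**What the plan says.** Study Objectives sets two linked aims. The first: "This project seeks to identify the neural and cognitive changes that accompany rapid relief from depressive symptoms following intravenous ketamine". The second: "We will then test whether these changes promote the uptake of helpful information delivered by a computer-based training protocol". The exposure in the second aim is therefore change.

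Under Analytic Plan, exploratory analysis 2 uses a "validated data-driven approach to identify integrative/combined moderators of CT effects (DV=MADRS slope" as the outcome, fitted by elastic net with cross-validation. Candidate moderators are taken "across all primary + exploratory indices (e.g., fMRI, HNK/BDNF levels, etc.) assessed after ketamine (n=100" patients), and the result is described as "defining the data-driven, integrative brain state that optimizes benefit from CT". The visit is not named. The 24-hour battery is the natural reading, because training starts on that day.

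The Summary of data collection timeline places the same kinds of measure before the infusion: "Screening/baseline procedures include pre-infusion psychiatric evaluation, medical screening, and assessment battery (depression/emotional functioning assessments, neuroimaging, cognitive tasks". It lists neuroimaging and cognitive tasks again at 24 hours. The documents do not say whether BDNF is sampled before infusion. HNK is a ketamine metabolite and has no pre-ketamine value.

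**The concern.** A 24-hour value is the pre-infusion value plus whatever happened since. A patient who already had a favourable fMRI signal or flexible cognition can show the same 24-hour value as one who moved there after the infusion. If training works better in patients with high 24-hour values, two explanations remain open: the change after ketamine helps training, or some patients were better training candidates beforehand. Only the first speaks to the second objective.

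What is at stake is interpretation. The primary tests are unaffected. But a reported optimal brain state after ketamine would readily be read as evidence about change, although the analysis as described has not looked at change.

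**Working it through.** **The plan's own figures.** For a two-arm comparison the noncentrality is d × √(n₁n₂/(n₁+n₂)).
- 100 vs 50, d = .49: .49 × 5.77 = 2.83. Two-sided power at .05 is 0.808 (normal) or 0.803 (t).
- 50 vs 50, d = .57: .57 × 5 = 2.85. Power is 0.813 or 0.806.

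Both stated values reproduce at 80% power. They concern arm comparisons; the plan gives no figure for the moderator analysis.

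**Which analysis uses what.**

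| Analysis | Patient-level neural, cognitive or biochemical index as moderator? | Baseline value of that index used? |
|---|---|---|
| Infusion phase: "Mixed models regression with timepoint (baseline, infusion+24-hours) as a continuous within-subject factor, drug condition (ketamine vs. saline) as a fixed between-subject factor" | No; compares mean change by drug | Yes, as outcome |
| Training phase, three arms, 24 hours to 30 days | No | No |
| Sensitivity analyses | No; sex, age, treatment resistance, medication | No |
| Exploratory analysis 2 | Yes, assessed after ketamine | Not named |

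**Closed form, one moderator.** Assume equal variances and baseline-to-24-hour correlation ρ (not in the documents, so a range is shown). Then corr(24-hour value, raw change)² = (1−ρ)/2. The noncentrality for 80% power at two-sided .05 is 2.80. It becomes 2.80 × √((1−ρ)/2) if the raw change is the true moderator and only the 24-hour value is tested. It becomes 2.80 × ρ if the pre-infusion trait is the true moderator.

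| ρ | Variance shared with change | Power for a true change moderator | Trait moderator flagged |
|---|---|---|---|
| .3 | 35% | 38% | 13% |
| .5 | 25% | 29% | 29% |
| .7 | 15% | 19% | 50% |
| .8 | 10% | 14% | 61% |

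**Simulation in 50 training + 50 sham ketamine patients** (2,000 runs per cell). The 24-hour value is ρ × trait + √(1−ρ²) × an independent part. The training effect varies by 0.57 or 0.8 outcome SD per SD of the moderator (assumed).

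Only the trait moderates; rate at which the 24-hour value is declared a moderator:

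| Test | Strength | ρ=.3 | .5 | .7 | .9 |
|---|---|---|---|---|---|
| 24-hour value alone | 0.57 | 12% | 24% | 45% | 68% |
| 24-hour value alone | 0.8 | 19% | 45% | 74% | 93% |

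With baseline by training in the model, the rate is 4–6% throughout if baseline is error-free. With baseline reliability 0.7 it is 7–34%, below the unadjusted rate in every cell. Raw change without baseline gives 5–59% over the same correlations, because change is itself correlated with baseline.

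If the independent part is the true moderator (strength 0.57), the 24-hour value alone finds it in 76%, 66%, 49% and 22% of runs at ρ = .3, .5, .7 and .9, against 77–78% with baseline in the model. Under this definition of change the loss is small at low ρ and large at high ρ. With baseline reliability 0.7 and ρ = .9, the adjusted test itself falls to 41%.

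In the adjusted linear model it does not matter whether the 24-hour value or the change is entered: b₁·pre + b₂·post = (b₁+b₂)·pre + b₂·(post−pre), so b₂ and its test are the same.

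**Elastic net check** (6 indices, 5-fold cross-validation, 150 runs, strength 0.8, only the trait moderates). With post values only, the trait-driven index was selected in 56%, 81% and 86% of runs at ρ = .5, .7, .9. Offering baseline values as extra candidates gave 29%, 42% and 63%. Entering baseline plus change left the change term selected in 31%, 31% and 28% at ρ = .5, .7, .8. Extra candidates help but do not settle attribution.

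**The case against.** Several points on the other side stand.

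- *The second objective has a randomised test.* The training-phase model compares ketamine + training, ketamine + sham and saline + training, which addresses the window hypothesis at group level. A reader might infer that the objective is untested; that is not so. What is missing is a link from the measured changes to training benefit.
- *The plan does not say ketamine-opened or ketamine-induced.* It says brain state. For asking who benefits from training after ketamine, the state when training starts is a legitimate predictor, and the analysis is labelled exploratory.
- *Level versus change is not stated.* The phrase about assessment after ketamine fixes timing. Raw post-infusion values are the likelier reading, not a stated fact. If change was intended, a sentence would settle it.
- *Other patient-level moderators are examined.* The sensitivity analyses cover demographic and clinical variables, though not baseline values of the indices.
- *A trait moderator would not show that ketamine is unnecessary.* A reader might infer this, but the trait could matter only under ketamine. Sham is given only to ketamine patients, so there is no saline + sham cell to tell.
- *Change within ketamine patients is not ketamine-induced change.* It also contains practice, expectancy, regression to the mean and drift since baseline.

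These points limit the claim and shape the remedy. They do not remove the ambiguity of a post-infusion value analysed without its baseline.

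**Conclusion.** The concern holds in a limited form. As described, exploratory analysis 2 cannot distinguish a change after ketamine from a pre-infusion trait, although the imaging, cognitive and self-report data that would help are already collected. This is an interpretive weakness in an exploratory analysis, and it leaves the primary comparisons intact.

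The percentages rest on a single-moderator test, a two-sided .05 level and an assumed correlation; the closed form also assumes equal variances. A varied response to ketamine could enlarge the 24-hour variance, raising its overlap with change and reducing the loss. It would be wrong to read the figures as error rates of the planned cross-validated multivariable model. They show direction and plausible size: the more stable the index, the more a post-infusion value reflects the trait.

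**What to change.** Keep the elastic net and add the following to the SAP.

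1. For each index measured both before infusion and at 24 hours (neuroimaging, cognitive tasks, self-report), pre-specify a conditional test in the 100 ketamine patients: 24-hour value (or change) by training, fitted together with baseline value by training and the main effects. Do not use change without baseline.
2. Describe an index as a post-infusion change that moderates training only if its term contributes beyond baseline. Otherwise report it as a predictor of training benefit after ketamine.
3. Do not call it ketamine-induced unless the infusion-phase time*drug test also shows a ketamine-versus-saline difference on that index.
4. Leave indices without a documented pre-infusion value as levels: HNK, and BDNF if not sampled before infusion.
5. Keep the analysis exploratory. A data-driven 50-versus-50 model should not be named as the test of the second objective.

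The cost is SAP text and more terms at n = 100; no new imaging or cognitive data are needed. Two limits remain. Misattribution persists where baseline is measured with error, and without a saline + sham cell the trial cannot show whether the moderation depends on ketamine.

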All infusions will be given over 40 minutes and administered in the MUH-CTRC by an experienced team with a linked ACLS-certified code team in a medical hospital setting, with safety/adverse event monitoring sustained for 4-hours post-infusion. Patient safety/decompensation will be monitored at every visit using appropriate exit/referral plans. Patients will be instructed to have nothing by mouth (except for water and coffee) the morning of the infusion and until 2 hours post-infusion.

Randomized, blinded, controlled trials provide the most rigorous method to test intervention effects at any level of analysis. A parallel arm design was selected for primary hypothesis tests due to previously observed cross-over effects in ketamine studies(114) and an anticipated increased risk of unblinding (for both ketamine and CT) if participants can directly compare treatment experiences (e.g., side effects, positive vs. neutral CT stimuli). 2:1 ketamine:saline followed by 2:1 CT:sham randomization was selected to increase probability of benefit to participants(115) and improve recruitment given substantial interest in ketamine from patients and referring clinicians, while maximizing statistical power for key comparisons: ket (n=100) vs. saline (n=50); ket+CT (n=50) vs. ket+sham (n=50) vs. saline+CT (n=50). A 1-month acute follow-up period is feasible and ethical for this initial efficacy study and, if supported, would have a clinically relevant impact, reducing safety and feasibility concerns regarding frequent infusions(28); 12m naturalistic follow-up will further characterize durability and inform frequency for future trials.

Participants will not be withdrawn from existing depression treatments (e.g., medications, therapy). They may continue in existing therapies for the duration of the study, provided they meet all inclusion/exclusion criteria.

Summary of data collection timeline:

The timeline below represents the target day for each set of procedures. At the PI's discretion, the precise day of assessments (e.g., number of days post-infusion) may be adjusted slightly in order to accommodate participant and research facility schedules.

All participants will undergo a medical screening and thorough psychiatric evaluation consisting of a structured diagnostic interview as well as self-report questionnaires to determine eligibility for study participation. Screening assessments for exclusion criteria:

- Initial phone screen

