Naturalistic follow-up visits will occur monthly in months 2-6 post-infusion and again at 12 months post-infusion. In addition to other assessments collected during the acute study period, a comprehensive, community treatment questionnaire will be administered to assess the type, dose and duration of medications, psychotherapy, other depression interventions and total inpatient/outpatient visits.

Eligibility Criteria:

Inclusion Criteria:

Participants will:

- 1) be between the ages of 18 and 60 years,

2) have not responded to one or more adequate trials of FDA-approved antidepressants within the current depressive episode, determined by Antidepressant Treatment History Form (ATHF) criteria [score ≥ 1]

3) score ≥ 25 on the Montgomery Asberg Depression Rating Scale (MADRS)(123)

4) score $>1SD$ above the normative mean on the Cognitive Triad Inventory (CTI(127)) “self” subscale(128,129), a well-validated self-report measure of maladaptive self-representations
OR $<1SD$ below the normative mean on the Rosenberg self-esteem scale, a widely used self-report measure of self-esteem

5) possess a level of understanding sufficient to agree to all tests and examinations required by the protocol and must sign an informed consent document

6) agree to sign a release of information (ROI), identifying another individual [friend, family member, etc.] as a contact person while the patient is enrolled in the study.

Exclusion Criteria:

1) Presence of lifetime bipolar, psychotic, or autism spectrum; current problematic substance use (e.g., substance use disorder); or lifetime recreational ketamine or PCP use

2) Use of a Monoamine Oxidase Inhibitor (MAOI) within the previous 2 weeks

3) Failure to meet standard MRI inclusion criteria: those who have cardiac pacemakers, neural pacemakers, cochlear implants, metal braces, or other non-MRI-compatible metal objects in their body, especially in the eye. Dental fillings do not present a problem. Plastic or removable dental appliances do not require exclusion. History of significant injury or surgery to the brain or spinal cord that would impair interpretation of results.

4) Current pregnancy or breastfeeding, or failure to engage in an effective birth control strategy throughout the duration of the study

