5) Acute suicidality or other psychiatric crises requiring treatment escalation. We will use the Columbia-Suicide Severity Rating Scale (C-SSRS; Version 1/14/09) as both an initial exclusion criteria (C-SSRS “Baseline/Screening” Version for past 1-month period) and as grounds for rescue/removal (C-SSRS “Since Last Visit” form). The C-SSRS will be administered using a paper form by an experienced and thoroughly trained clinical assessor on the study team. Subjects with C-SSRS suicide ideation scores scored “yes” on items 4 (active suicidal ideation with some intent to act) and/or 5 (active suicidal ideation with specific plan and intent) will be excluded from the study, and if enrolled, will be exited from the study and referred immediately

to the nearest emergency mental health facility for additional thorough assessment and appropriate treatment referral.

- 6) Changes made to treatment regimen within 4 weeks of baseline assessment
- 7) Reading level <6th grade as per patient self-report
- 8) For study entry, patients must be reasonable medical candidates for ketamine infusion, as determined by a board-certified physician co-investigator during study Screening. Serious, unstable medical illnesses including respiratory [obstructive sleep apnea, or history of difficulty with airway management during previous anesthetics], cardiovascular [including ischemic heart disease and uncontrolled hypertension], and neurologic [including history of severe head injury] will be exclusions.
- 9) Clinically significant abnormal findings of laboratory parameters [including urine toxicology screen for drugs of abuse], physical examination, or ECG.
- 10) Uncontrolled or poorly controlled hypertension, as determined by a board-certified physician co-investigator's review of vitals collected during screening and any other relevant medical history/records.
- 11) Patients with one or more seizures without a clear and resolved etiology.
- 12) Patients starting hormonal treatment (e.g., estrogen) in the 3 months prior to Screening.
- 13) Past intolerance or hypersensitivity to ketamine.
- 14) Patients taking medications with known activity at the NMDA or AMPA glutamate receptor [e.g., riluzole, amantadine, memantine, topiramate, dextromethorphan, D-cycloserine], or the mu-opioid receptor.
- 15) Patients taking any of the following medications: St John's Wort, theophylline, tramadol, metrizamide
- 16) Patients who have received ECT in the past 6 months prior to Screening.

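### The suicidality exit rule has no time limit and does not separate stopping treatment from stopping follow-up, so a day-21 exit would only lose later outcome data (low priority)

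*Combined protocol and SAP*

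**What the plan says.** Exclusion Criterion 5 (Eligibility Criteria) uses the C-SSRS twice: at screening, and after enrolment, with the form covering the time since the last visit, "as grounds for rescue/removal". A patient with a yes on ideation item 4 or 5 "will be excluded from the study, and if enrolled, will be exited from the study and referred immediately" for emergency assessment. No time window is given. Study Design & Methods adds: "Patient safety/decompensation will be monitored at every visit using appropriate exit/referral plans". Those plans are not set out.

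The Summary of data collection timeline gives one infusion, then training as "eight 15-20min sessions completed 2x/day (sessions separated by >=20 min) on days 1-4 post-infusion", with suicidality assessed alongside. Suicidality is next listed at "Infusion +21 days remote (questionnaire/phone) assessment (depression and suicidality assessments"). After that come "Infusion +30-days assessment battery (depression/emotional functioning assessments, neuroimaging, cognitive tasks") and six remote naturalistic contacts at months 2, 3, 4, 5, 6 and 12. The naturalistic phase adds a community treatment questionnaire covering medication, psychotherapy, "other depression interventions and total inpatient/outpatient visits".

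The Analytic Plan models the training phase from 24 hours to 30 days. Exploratory analysis 1 extends the depression model to 12 months with the QIDS-SR. Study Design & Methods says that "12m naturalistic follow-up will further characterize durability and inform frequency for future trials".

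**The concern.** The trial asks whether rapid relief lasts. A patient who reports active suicidal ideation with intent at day 21 is one whose relief has clearly failed. Stopping treatment on that signal is sensible while treatment is running, but at day 21 none is left to stop. If the exit also ends data collection, the plan drops such patients from day 30 and from the year of follow-up that is meant to describe durability, for a reason tied to the outcome. It also loses their record of rescue care, which the community treatment questionnaire is designed to capture. The Analytic Plan does not say how data missing after an exit are handled. Under the Sample Size section such a patient has normally completed enough training to count toward the 150, and so would not be replaced.

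**Working it through.** **Schedule count.** Target days and months are from the Summary of data collection timeline.

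- Last study treatment: day 4. Day-21 contact: 21 − 4 = 17 days later.
- Assessments after day 21: 1 (day 30) + 6 (months 2, 3, 4, 5, 6, 12) = 7.
- Lost by a day-21 exit, read plainly: 7 of 7. Kept: everything up to day 21. On the natural reading this includes the day-21 depression score, because the timeline pairs it with the suicidality assessment.

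**The plan's power figure (background, not disputed).** For 50 vs 50, d = .57 and two-sided α = .05, the noncentrality is .57 × √(50/2) = 2.85, giving 80.6% power (t-test). This agrees with the stated 80%.

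**Effect on the arm comparison.** The documents give no exit rate, SD or size of worsening, so all of these are assumed:

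- Model: y = a(arm) + b(arm) × day + u + e, with SD(u) = 6 and SD(e) = 5; 50 patients per arm.
- The comparator arm worsens by 0.15 points/day, so the day-30 difference before crises is 0.15 × 30 = 4.50.
- A crisis adds 10 points at day 21 and 10 × (1 − rescue) at day 30. Exit removes day 30 only.
- Contacts: days 1, 2, 3, 4, 5, 7, 12, 21, 30.

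Within each arm the expected fit is b̂ = (Σ wX′V⁻¹X)⁻¹ Σ wX′V⁻¹μ, summed over data patterns with proportions w. The fitted day-30 value is (1, 30)b̂. The SE of the day-30 difference with complete data is 1.445. Exits are given as comparator arm vs better arm; 6% vs 2% of 50 is 3 vs 1 patients. Shifts are taken before rounding.

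| Exits | Rise after crisis | All kept | Exited | Shift in SE |
|---|---|---|---|---|
| 6% vs 2% | persists | 4.92 | 4.70 | 0.15, smaller |
| 6% vs 2% | halved | 4.79 | 4.70 | 0.06, smaller |
| 6% vs 2% | removed | 4.67 | 4.70 | 0.03, larger |
| 6% vs 6% | any | 4.50 | 4.50 | 0 |
| 2% vs 6% | persists | 4.08 | 4.30 | 0.15, larger |
| 4% vs 2% | persists | 4.71 | 4.60 | 0.08, smaller |
| 10% vs 2% | persists | 5.35 | 4.92 | 0.30, smaller |

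**Partial retention.** The 'all kept' column assumes that every crisis patient supplies day 30. If half do, 6% vs 2% gives 4.82 against 4.70 (0.08 SE) with a persistent rise, and 4.75 against 4.70 (0.03 SE) with the rise halved.

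**Which contacts carry the outcome.** The timeline does not name the scale at each contact, so the set was varied (6% vs 2%, persistent rise, all kept vs exited):

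- without day 7: 4.93 vs 4.71, 0.15 SE;
- days 1, 5, 12, 21, 30: 4.93 vs 4.73, 0.14 SE;
- days 1, 5, 12, 30 only, so that the triggering score is not in the model: 4.86 vs 4.50, SE 1.53, 0.24 SE.

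**The case against.** The strongest reply is that the harm is inferred. The criterion sits in an eligibility list and says that patients are exited, not that data collection stops. Its phrase "as grounds for rescue/removal" does not say what the patient is removed from. The exit/referral plans are not reproduced and the consent pages are not visible; either could already allow later contact. This stands, and it limits the point to what the visible text says.

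The trigger at day 21 is also partly inferred. The criterion describes a paper C-SSRS given by a trained assessor, while day 21 is remote and no scale is named. Use of the C-SSRS there is plausible, given its post-enrolment role and the monitoring at every visit, but it is not stated.

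The planned mixed model uses all scores up to the exit, at most one acute contact is lost, and the six later contacts feed only an exploratory analysis and a description of later care. Exit also spares a patient in crisis further research demands, including a day-30 battery with neuroimaging. These points stand too. They bear on priority and on the form of the fix; they do not recover the later course or the rescue care.

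A reader might infer two stronger claims. One is that the rule materially biases the treatment effect, probably towards no difference. The documents do not support this: no exit rates are given, and the shift vanishes with equal exits and reverses with reversed exits. The other is a real loss of power. For a single day-30 contrast at d = .57, power would fall from 80.6% to 78.9% with 4% exits per arm, 76.2% with 10% and 71.2% with 20%. Those rates are only illustrations, and a single-point contrast overstates the loss for a repeated-measures model.

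**Conclusion.** The point holds as a cheap, low-priority improvement. As written, the rule has no time limit and does not separate stopping treatment from stopping follow-up. Applied at day 21 it protects no one beyond what the referral already does, and read plainly it loses seven of seven remaining assessments.

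The effect on the arm comparison is small and its direction is not established. With assumed exits of 6% vs 2% on the nine-contact schedule it is at most about 0.15 SE, and about 0.08 SE if half of these patients supply day 30. It reaches 0.24 SE if the day-21 score is not in the model, and 0.30 SE in the more extreme 10% vs 2% case. The SDs, the exit rates, the 10-point rise and the rescue effect are all assumptions.

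The main loss is descriptive: what happens to the patients whose relief failed, and what care they then need. The conclusion rests on reading 'exited' as the end of data collection and on the C-SSRS being used at day 21.

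**What to change.** Keep the threshold, the immediate referral and the stopping of any remaining training sessions. In Criterion 5, replace the exit wording with *discontinued from study intervention*. Then:

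- record the depression score at the contact that triggers the rule;
- continue voluntary outcome collection on the existing schedule, mainly the remote QIDS-SR and the community treatment questionnaire, with day-30 depression ratings where feasible and no requirement for neuroimaging;
- analyse these patients in their randomised arm and report the events by arm.

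The cost is a short protocol and consent amendment. With 4 exits the extra work is at most 4 × 6 = 24 remote contacts and 4 day-30 assessments. With 3 exits in each of three arms it is 9 × 6 = 54 and 9. All of these are already scheduled. The contact-person release in Inclusion Criterion 6 covers only the period of enrolment and would need extending if it is used after the crisis.

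The downside is a small burden on a few patients in crisis. Voluntary collection will not remove all outcome-related missing data, since those who respond may be the better recovered. If the exit/referral plans or the consent form already allow follow-up after exit, only the wording of Criterion 5 needs aligning.
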